### 7.2.3 Per Protocol Analysis Set

The per protocol analysis set (PP) will include all subjects in the FAS who had no major protocol violation that would impact significantly on the primary efficacy endpoint. The list of major protocol deviations will be finalized prior to database lock. All decisions to exclude subjects from the PP analysis set will be made prior to unblinding in the final blinded data review (BDR) meeting and report. Data will be summarized and analyzed according to the treatment a subject actually received at randomization.

### 7.2.4 Population Pharmacokinetic Analysis Set

The population pharmacokinetic analysis set (PPK) will include all subjects who receive at least one dose of study medication and who provide at least one post dose concentration sample for the Population PK analysis. All analyses using the PPK set will group subjects according to treatment actually received.

## 7.3 Primary Endpoints

### 7.3.1 Definition of Primary Endpoints

The primary efficacy endpoint is the change from baseline trough FEV1 on Day 85.

- Baseline FEV1 is defined as the average of the -45 and -15 minute measurements prior to dosing of study medication on Day 1 (Visit 3).
- Trough FEV1 measurements will be the pre-dose FEV1 measures on Day 29, 57 and 85 calculated as the average of the -45 and -15 minute measurements prior to dosing of study medication.
- If a public health emergency prevents FEV1 data from being measured at site then information on the reasons for the missing assessments will be recorded in the CRF.

### 7.3.2 Statistical Methodology for Primary Endpoints

The analysis of the primary endpoint will be based on a mixed model repeated measures (MMRM) analysis including changes from baseline trough FEV1 measurements on Days 29, 57 and 85 as the dependent variable. The model will include independent fixed-effect terms for concomitant LABA use, reversibility to ipratropium, smoking status, age, sex, treatment and baseline FEV1 as a covariate. A time effect (visit) and its interaction terms with treatment and baseline FEV1 will be included. The variance estimation will be based on an unstructured covariance matrix. The Kenward-Roger method for approximating the denominator degrees of freedom will be used.

### 7.3.3 Primary Analysis for Primary Endpoint

The primary analysis of the primary efficacy endpoint will be based on the FAS population and includes all randomized subjects who received at least one dose of study drug and have at least one recorded post-baseline FEV1 assessment. Available data for a subject prior to discontinuing study treatment will be used in the MMRM analysis. Missing data is assumed as missing at random (MAR). The robustness of the conclusions to this assumption will be assessed with a missing data sensitivity analysis.

The difference between refefenacin and placebo on Day 85 will be estimated from the least squares means (LSmeans) along with the 95% confidence interval (CI) and associated 2-sided p-values.

### 7.3.4 Secondary/Sensitivity Analyses for Primary Endpoint

The same primary analysis model will be replicated in the PP population.

A sensitivity analysis using a two-dimensional tipping point imputation method will be applied to the MMRM analysis (FAS population) to assess the robustness of the conclusions to the assumption that missing data is MAR. In the tipping point analysis a succession of delta adjustments via multiple imputation methods will be used to impute the missing refefenacin and placebo trough FEV1 values at each timepoint. The tipping point is denoted as the mean trough FEV1 value that would have to be imputed to overturn a statistically

significant result. Clinical judgement will be applied to the plausibility of the tipping point. The detail of the imputation method will be included in the SAP.

In addition, missing trough FEV1 data on Day 85 will be imputed using a Last-Observation-Carried-Forward (LOCF) single imputation method. Change from baseline FEV1 at Day 85 will be analyzed using an analysis of covariance (ANCOVA) using the FAS population. The model will include independent fixed-effect terms for concomitant LABA use, reversibility to ipratropium, smoking status, age, sex, treatment and baseline FEV1 as a covariate.

LSmeans for Day 85 will be derived for both treatment groups. The difference between rевеfенасin and placebo on Day 85 will be estimated from the LSmeans along with the 95% CI and associated 2-sided p-values.

### 7.3.5 Missing Data

Missing imputed data methods will be performed in the primary and sensitivity analyses as described above for trough FEV1. Otherwise, missing data will not be imputed.

### 7.3.6 Sub-Group Analyses

For the primary endpoint the follow subgroups are pre-defined for the purpose of sensitivity analyses:

- Baseline smoking status [current smoker, ex-smoker]
- Age group [<65, >=65 years]
- Sex [Male, Female]
- Reversibility to ipratropium [yes, no]
- Concomitant ICS use [yes, no]
- Concomitant LABA use [yes, no]
- Baseline post bronchodilator % predicted FEV1 [50% to <80%, 30% to <50%, <30%]
- GOLD categories [A, B, C, D]

Forest plots will be produced for these subgroups. Additional subgroups and analyses may be defined in the SAP.

## 7.4 Secondary Efficacy Endpoints

In all the secondary efficacy analyses missing data will not be imputed and will be assumed to be missing at random (MAR). Secondary efficacy analyses will be performed using the FAS population. If a public health emergency prevents data from being measured or requires data to be assessed remotely via a virtual visit, then information on the reasons and the data impacted will be recorded in the CRF.

### 7.4.1 Spirometry

#### 7.4.1.1 Trough FEV1 on Days 29 and 57

The changes from baseline trough FEV1 on Days 29 and 57 will be estimated from the MMRM analysis used for the primary analysis of the primary endpoint.

#### 7.4.1.2 Trough FVC on Days 29, 57 and 85

The changes from baseline trough FVC on Days 29, 57 and 85 will be analyzed using the same MMRM analysis described for the primary analysis of the primary endpoint. The baseline FEV1 covariate will be replaced with the baseline trough FVC recorded on Day 1.

#### 7.4.1.3 Peak FEV1 (0-2h) on Day 1 and Day 85

Lung function assessments will be made after study treatments (5, 15, and 30 minutes, and 1, 1.5, and 2 hours) on Days 1 and 85.

Analysis of Covariance (ANCOVA) model will be used to assess the difference between treatment groups for change from baseline Peak FEV1 after the first dose on Day 1. The ANCOVA model will include fixed-effect terms for concomitant LABA use, reversibility to ipratropium, smoking status, age, sex, treatment and baseline FEV1 as a covariate.

The difference between refefenacin and placebo on Day 1 will be estimated from the LSmeans along with the 95% CI and associated 2-sided p-values.

A separate analysis will be performed for Peak FEV1 on Day 85 using the same ANCOVA model.

#### 7.4.1.4 Weighted Mean FEV1 (0-2h) on Day 1 and Day 85

Lung function assessments will be made after study treatments (5, 15, and 30 minutes, and 1, 1.5, and 2 hours) on Days 1 and 85.

The area under the curve (AUC), (0 to 2h) will be calculated using the trapezoidal rule including observed data points from pre-dose (0 hours) through to the 2 hour observation. For all observations the nominal time of the observation should be used. For the calculation of AUC, the first, last and at least one time point between first and last must be available. Otherwise, the AUC is set to missing.

The weighted mean (WM) FEV1 is derived by dividing AUC by the total time (nominally 2 hours).

An ANCOVA model will be used to assess the difference between treatment groups for WM FEV1 on Day 1 and Day 85 in separate models. Each ANCOVA model will include fixed-effect terms for concomitant LABA use, reversibility to ipratropium, smoking status, age, sex, treatment and baseline FEV1 as a covariate.

The difference between refefenacin and placebo on Day 1 and Day 85 will be estimated from the LSmeans along with the 95% CI and associated 2-sided p-values.

### 7.4.2 Patient Reported Outcomes (PROs)

#### 7.4.2.1 SGRQ on Day 85 (continuous endpoint)

Baseline SGRQ endpoints will be those recorded on Day 1. The change from baseline SGRQ scores on Day 85 will be summarized and analyzed as a continuous endpoint.

An ANCOVA model will be used to assess the difference between treatment groups for change from baseline SGRQ on Day 85. The ANCOVA model will include fixed-effect terms for concomitant LABA use, reversibility to ipratropium, smoking status, age, sex, treatment and baseline SGRQ as a covariate. For subjects who discontinue study treatment, the data from the SGRQ completed at the Early Termination (ET) visit will be carried forward in the analyses.

The difference between refefenacin and placebo on Day 85 will be estimated from the LSmeans along with the 95% CI and associated 2-sided p-values.

#### **7.4.2.2 SGRQ Responders (total score $\geq 4$ units) on Day 85**

A decrease from baseline of  $\geq 4$  units in SGRQ total score is considered clinically meaningful and will be defined as a responder.

The number and percentage of responders on Day 85 in each treatment group will be summarized. A comparison between refefenacin and placebo will be evaluated with the odds ratio (OR) and corresponding 95% confidence interval from a logistic regression model. The model will include fixed-effect terms for concomitant LABA use, reversibility to ipratropium, smoking status, age, sex, treatment and baseline SGRQ total score as a covariate.

For subjects who discontinue study treatment, the SGRQ completed at the Early Termination (ET) visit will be carried forward and used to derive a responder.

#### **7.4.2.3 BDI/TDI on Days 29, 57 and 85**

Baseline BDI score will be recorded on Day 1. The TDI represents changes from baseline and will be recorded on Days 29, 57 and 85.

The TDI focal score will be analyzed using the same MMRM analysis described for the primary analysis of the primary endpoint. The baseline FEV1 covariate will be replaced with the BDI focal score. Estimates for TDI on Days 29, 57 and 85 will be derived from the model.

The difference between refefenacin and placebo on Days 29, 57 and 85 will be estimated from the LSmeans along with the 95% CI and associated 2-sided p-values.

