#### **7.4.2.4 TDI Responders (focal score $\geq 1$ unit) on Days 29, 57 and 85**

A TDI focal score of  $\geq 1$  unit is considered clinically meaningful and will be defined as a responder.

The number and percentage of responders on Days 29, 57 and 85 in each treatment group will be summarized. A comparison between refefenacin and placebo will be evaluated with the odds ratio (OR) and corresponding 95% confidence interval from a logistic regression model including the proportion of responders at each visit (Days 29, 57 and 85) as the dependent variable. The MMRM logistic model will include the same independent fixed-effect terms as for the primary analysis of the primary endpoint. The baseline FEV1 covariate will be replaced with the BDI focal score as a covariate. Estimates for the proportion of TDI responders on Days 29, 57 and 85 will be derived from the model.

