### Change in Functional Impairment

Ask the patient to recall his or her breathlessness at the first or baseline visit, or you may describe this information (from the BDI) to the patient.

Ask whether there has been any change since the first or baseline visit. Any activities started or stopped? Any modifications in job/work activities?

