## PART II: BDI

### Functional Impairment

\_\_\_\_\_ Grade 4: No Impairment. Able to carry out usual activities and occupation without shortness of breath.

\_\_\_\_\_ Grade 3: Slight Impairment. Distinct impairment in at least one activity but no activities completely abandoned. Reduction, in activity at work or in usual activities, that seems slight or not clearly caused by shortness of breath.

\_\_\_\_\_ Grade 2: Moderate Impairment. Patient has changed jobs and/or has abandoned at least one usual activity due to shortness of breath.

\_\_\_\_\_ Grade 1: Severe Impairment. Patient unable to work or has given up most or all usual activities due to shortness of breath.

\_\_\_\_\_ Grade 0: Very Severe Impairment. Unable to work and has given up most or all usual activities due to shortness of breath.

\_\_\_\_\_ W: Amount Uncertain. Patient is impaired due to shortness of breath, but amount cannot be specified. Details are not sufficient to allow impairment to be categorized.

\_\_\_\_\_ X: Unknown. Information unavailable regarding impairment.

\_\_\_\_\_ Y: Impaired for Reasons Other than Shortness of Breath. For example, musculoskeletal problem or chest pain.

Usual activities refer to requirements of daily living, maintenance or upkeep of residence, yard work, gardening, shopping, etc.

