The BDI and TDI focal scores and associated components will be listed and summarized by treatment and visit using summary statistics. Baseline BDI scores will be recorded on Day 1 (Visit 3). The TDI questionnaire represents changes from baseline and will be recorded on Days 29, 57 and 85.

The BDI/TDI scores include three components: functional impairment, magnitude of task, and magnitude of effort. For BDI scores, each domain can be rated from Grade 0 (very severe) to 4 (no impairment). For TDI scores, each domain can be rated from Grade -3 (major deterioration) to + 3 (major improvement). The focal score is the sum of the three components (ie BDI ranges from 0 to 12 and TDI ranges from -9 to +9).

The TDI focal score will be analyzed using the same MMRM analysis described for the primary analysis of the primary endpoint. The baseline  $FEV_1$  covariate will be replaced with the BDI focal score. Estimates for TDI on Days 29, 57 and 85 will be derived from the model.

The difference between revefenacin and placebo on Days 29, 57 and 85 will be estimated from the LSmeans along with the 95% CI and associated 2-sided p-values.

The three TDI components will be analyzed in a similar way.

Details of BDI/TDI are further described in Section 6.6.

4.10.3.7 Number (%) of TDI Responders (Focal Score ≥1) on Days 29, 57 and 85

A TDI focal score of  $\geq 1$  unit is considered clinically meaningful and will be defined as a responder.

The number and percentage of responders on Days 29, 57 and 85 in each treatment group will be summarized. A comparison between revefenacin and placebo will be evaluated with the odds ratio (OR) and corresponding 95% confidence interval from a logistic regression model

including the proportion of responders at each visit (Days 29, 57 and 85) as the dependent variable. The MMRM logistic (binomial distribution with logit link function) model will include the same independent fixed-effect terms as for the primary analysis of the primary endpoint. The baseline FEV1 covariate will be replaced with the BDI focal score as a covariate. Estimates for the proportion of TDI responders on Days 29, 57 and 85 will be derived from the model.

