## 6.6 BDI/TDI Component Score and Focal Score

Dyspnea Index (BDI) measures the severity of dyspnea at the beginning of the trial and the Transition Dyspnea Index (TDI) evaluates changes from this baseline (transition period). The BDI as well as the TDI are composed of the three categories: Functional Impairment, Magnitude of Task, Magnitude of Effort.

The BDI includes five grades of severity from zero (very severe impairment) to four (no impairment) and the categories are summed to create the focal score (zero to twelve).

The TDI ranges from minus three (major deterioration) to plus three (major improvement) including a zero score to indicate "no change". Also for the TDI the three categories are added to obtain a focal score ranging from minus nine, including zero, to plus nine. Provision is made for circumstances when dyspnea cannot be rated: in the BDI, score "X" if no information on the severity can be obtained, "W" if there is generally insufficient information, or "Y" if the patient's capacity is compromised by factors other than respiratory. In the TDI, score "Z" if reduction of activities, effort or functional impairment is caused by reasons other than respiratory.

If a component score is missing or scored W, X, Y, Z then the focal score will be set to missing.

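### No fallback for a missing BDI focal score: subjects with a valid TDI but an ungraded BDI component leave the fitted TDI models

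*Protocol*

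**What the plan says.** **Covariate.** For the TDI focal score, Protocol 7.4.2.3 reuses the primary MMRM, in which baseline FEV1 appears both as a covariate and in an interaction with visit. The FEV1 "covariate will be replaced with the BDI focal score. Estimates for TDI on Days 29, 57 and 85 will be derived from the model". For TDI responders, Protocol 7.4.2.4 says the FEV1 "covariate will be replaced with the BDI focal score as a covariate", and SAP 4.10.3.7 agrees: "The baseline FEV1 covariate will be replaced with the BDI focal score as a covariate".

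**Scoring.** SAP 6.6: "If a component score is missing or scored W, X, Y, Z then the focal score will be set to missing". The BDI form in Protocol 11.1 offers ungraded answers on each of its three components, for example "W: Amount Uncertain. Patient is impaired due to shortness of breath, but amount cannot be specified" and "Y: Impaired for Reasons Other than Shortness of Breath. For example, musculoskeletal problem or chest pain". Code X covers unavailable information.

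**Missing data.** Protocol 7.4: "In all the secondary efficacy analyses missing data will not be imputed". SAP 4.10.1.3 confines imputation to the sensitivity analyses of the primary endpoint. SAP 4.10.3 leaves room for stated exceptions but states none for the BDI.

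**Analysis set.** SAP 4.5 uses the FAS for all efficacy endpoints. Entry needs randomization, one dose and one post-baseline efficacy assessment; a baseline BDI is not required.

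**The concern.** The TDI is rated directly as change, so its focal score can be computed without a BDI total. The BDI total enters the models only for adjustment. A mixed or logistic model cannot use a record whose covariate is missing. Because the BDI is a baseline value, one ungraded component removes all of that subject's TDI visits from the fit.

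TDI on Day 85 is a listed secondary endpoint. The plan assigns it to the FAS, yet its rules applied as written would fit it on a smaller set, discarding observed outcomes of randomized subjects because an adjustment variable is missing.

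**Working it through.** **1. Can a valid TDI exist without a BDI focal score?** Yes. The TDI instructions in Protocol 11.1 tell the interviewer: "Ask the patient to recall his or her breathlessness at the first or baseline visit", or to describe the baseline state to the patient; referring back to BDI grades is only recommended. The functional-impairment and effort items are worded without reference to BDI grades. The task item is different: its moderate and major categories count grades moved from baseline. The TDI also has its own unrateable code, Z, for further impairment from other causes.

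**2. Does another rule rescue the covariate?** None was found.
- The general baseline rule (SAP 4.3.2) takes the latest pre-dose value, but the BDI is scheduled only once, at Visit 3.
- Baseline FEV1 is protected: a valid reading is a randomization criterion (Protocol 4.2.3), one of the two pre-dose readings suffices, and without a baseline the change score is missing anyway (SAP 4.10.2). That covariate therefore costs no extra subjects.
- The SGRQ tolerates missed items (SAP 6.7.3). The BDI has no tolerance.

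**3. The plan's own design figures.** These are for trough FEV1 only: 100 mL, SD 245 mL, two-sided 5%, 90% power. The normal formula gives 127 per arm; the t-test gives 89.98% power at 127 and 90.2% at 128, so 128 per arm reproduces. Then 256/0.80 = 320. The documents give no power figure for TDI, so the 80% below is illustrative.

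**4. Size.** Assumption: a proportion p of ungraded answers per BDI component, 1-3%. The share f of subjects without a BDI focal score is p if ungraded answers fully cluster within subjects, and 1-(1-p)³ if components are independent. The SE rises by 1/√(1-f) - 1. Power starting from 80% becomes Φ(2.802·√(1-f) - 1.960).

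| p | Pattern | f | Of 320 | SE rise | 80% power becomes |
|---|---|---|---|---|---|
| 1% | clustered | 1.0% | 3.2 | 0.5% | 79.6% |
| 3% | clustered | 3.0% | 9.6 | 1.5% | 78.8% |
| 1% | independent | 1-0.99³ = 3.0% | 9.5 | 1.5% | 78.8% |
| 2% | independent | 1-0.98³ = 5.9% | 18.8 | 3.1% | 77.6% |
| 3% | independent | 1-0.97³ = 8.7% | 27.9 | 4.7% | 76.3% |

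These are upper limits under the stated rates, because they treat every subject without a BDI focal score as having usable TDI data. If the task component is left out because the TDI task item leans on the baseline grade, two independent components give 1-0.99² = 2.0% to 1-0.97² = 5.9% (about 6-19 of 320). On the 256 evaluable subjects, the 8.7% row is about 22.

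**5. Does filling in the covariate recover the loss?** An illustrative linear ANCOVA was simulated 1,000 times (assumed: N = 320, effect 0.7, residual SD 2.5, about 6% of BDI scores missing, more often in the more breathless).

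| Handling | Subjects used | SE | Power | Mean estimate |
|---|---|---|---|---|
| Deletion | 300 on average | 0.288 | 65.9% | 0.69 |
| Mean fill-in | 320 | 0.280 | 69.1% | 0.69 |
| Complete BDI | 320 | 0.279 | 69.3% | 0.69 |

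This covers the linear, single-visit case. The logistic model was not simulated.

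**The case against.** The strongest reply is that the effect may be negligible. No rate of ungraded answers is given. A patient limited by, say, a joint problem would probably be coded Y on several components, so independence overstates the count. Missing data are queried, and the BDI interview is built to reach a grade. Some affected subjects will have no valid TDI to lose, through dropout, code Z or a task item with no baseline grade to count from. Complete-case handling of a baseline covariate is also a common default. All of this limits the size, and the range above allows for clustering. It does not supply the missing rule.

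The deletion itself is standard software behaviour and is not stated in the plan. The sample SAS code for these models is not in the text available for review, so handling at code level could not be checked.

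A reader might infer more than the documents support:
- **That the treatment comparison is biased.** The BDI is completed at Visit 3 before randomization (Protocol 6.2.1), so loss should be balanced between arms on average. The simulated estimate was the same under deletion and fill-in.
- **That those lost are mainly patients with comorbid limitation, so the result describes a distinct, narrower population.** Codes W and X concern uncertain or unavailable information, and nothing shows how the codes would divide.
- **That all TDI results are affected.** Descriptive summaries and responder counts do not use the BDI focal score.

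**Conclusion.** The gap is real and minor. As written, the two fitted TDI models omit FAS subjects who have a valid TDI focal score but no BDI focal score, and the plan states no alternative. At an assumed 1-3% ungraded rate per component, the share without a BDI focal score is 1-3% with full clustering and 3-9% with independence, about 3-28 of 320. The SE rises by about 0.5-4.7%, and an illustrative 80% power falls to about 79.6-76%. The true loss should be below these figures if the assumed rates hold, since not every such subject will have a TDI score. The consequence is a small loss of precision and an undeclared departure from the FAS. It does not touch the primary endpoint.

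**What to change.** In SAP 4.10.3.6, 4.10.3.7 and 6.6, state that in the TDI models only, a missing BDI focal score is replaced by the mean BDI focal score of the FAS, pooled over both arms and calculated without reference to treatment. The same value serves in the covariate-by-visit interaction. The TDI outcome stays unimputed. Report the number of subjects filled in by arm, and give the complete-case result as a sensitivity analysis.

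The cost is a sentence in the SAP, a line of code and one extra output. Covariate adjustment is slightly weaker for the filled-in subjects. In the responder model this may shift the conditional odds ratio marginally, which is why the complete-case result should sit beside it. The rule should be set before unblinding; under SAP 4.13, a change made after SAP version 2.0 is finalized is documented in the clinical study report.
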